**5.2. Criteria for eliminating data from Analysis Sets**

Elimination codes are used to identify subjects to be eliminated from analysis. Details are provided below for each set.

**5.2.1. Elimination from Exposed Set (ES)**

Code 1030 (Study vaccine not administered at all) and code 900 (invalid informed consent or fraud data) will be used to identify subjects eliminated from ES.

A subject will be excluded from the safety analysis under the following conditions

Code	Condition under which the code is used
900	Invalid informed consent or fraud data
1030	Study vaccine not administered at all
1150	No post-vaccination safety data
1160	No solicited safety data

**5.2.1.1. Elimination from Solicited Safety Set**

Code 1030, code 900 and code 1160 will be used to identify subjects eliminated from the Solicited Safety Set. Code 1070 will be used to identify subjects eliminated from the Solicited Safety Set by visit when vaccination is not administered at that visit.

**CONFIDENTIAL**207759 (NTHI MCAT-008)  
Statistical Analysis Plan Amendment 1 Final**5.2.1.2. Elimination from Unsolicited Safety Set**

Code 1030, code 900 and code 1150 will be used to identify subjects eliminated from the Unsolicited Safety Set.

Code 1150 will be attributed to subjects if all the following conditions are met:

- did not complete the safety assessment following the 7-day follow-up period after each vaccination (i.e. phone contacts),
- did not return any paper Diary after each vaccination,
- did not return for the scheduled visit 30-days after each vaccination,
- did not report any unsolicited AE.

Code 1070 will be used to identify subjects eliminated from the Solicited Safety Set by visit when vaccination is not administered at that visit.

**5.2.2. Elimination from Full analysis Set (FAS)****5.2.2.1. Excluded subjects**

A subject will be excluded from the FAS analysis under the following conditions

Code	Condition under which the code is used
900	Invalid informed consent or fraud data
1030	Study vaccine not administered at all
2100.a	Serological results not available after all vaccination (for Antibody determination)
2100.b	Serological results not available after all vaccination (for CMI responses)

**CONFIDENTIAL**207759 (NTHI MCAT-008)  
Statistical Analysis Plan Amendment 1 Final**5.2.3. Elimination from Per-protocol analysis Set (PPS)****5.2.3.1. Excluded subjects**

A subject will be excluded from the PPS analysis under the following conditions

Code	Condition under which the code is used
900	Invalid informed consent or fraud data
1030	Study vaccine not administered at all
1040	Administration of concomitant vaccine(s) forbidden in the protocol*
1050	Randomization failure
1060	Randomization code was broken
1070	Vaccination not according to protocol
1080	Vaccine temperature deviation
1090	Expired vaccine administered
2010	Protocol violation (inclusion/exclusion criteria)**
2030	Laboratory values outside range before any vaccination (for Antibody determination)
2040	Administration of any medication forbidden by the protocol*
2050	Medical condition forbidden by the protocol
2080	Subjects did not comply with vaccination schedule
2090	Subjects did not comply with blood sample schedule (for Antibody determination)
2100	Serological results not available post-vaccination (for Antibody determination)
2120	Obvious incoherence or abnormality or error in lab data (for Antibody determination)
2130	Subject not planned to be bled for their all blood sampling visits

\*See protocol sections 6.6.1 and 6.6.2 for specific details.

\*\*See protocol sections 4.2 and 4.3 for specific details.

\*\*\* See Study Procedure Manual for details.

**5.2.3.2. Right censored Data**

Data from a subject will be censored from visit x for the PPS analysis under the following conditions. The code \*\*\*\*.X+ will also be used to identify study withdrawal from visit x.

Code	Condition under which the code is used
1040.x+	Administration of concomitant vaccine(s) forbidden in the protocol
1060.x+	Randomization code was broken
2040.x+	Administration of any medication forbidden by the protocol

**5.3. Important protocol deviation not leading to elimination from per-protocol analysis set**

The following important protocol deviations will be reported by groups:

- Forced randomization: in case of supplies shortage for the next assigned vaccine according to the randomization schedule at the clinical site, the randomization system will use the forced randomization procedure in order to continue to enrol and vaccinate subjects. The system moves seamlessly to the next treatment/randomization number for which vaccine supplies are available. The site will not be aware of the forced randomization event.

**CONFIDENTIAL**

207759 (NTHI MCAT-008)

Statistical Analysis Plan Amendment 1 Final

- Manual randomization: in case the randomization system is unavailable, the investigator has the option to perform randomization by selecting supplies available at the site according to a pre-defined rule.
- In case unexpected vaccinations at study start were granted due to regulatory recommendation, the subjects who had such vaccination might be mentioned.
- Subjects of childbearing potential without pregnancy test for whom the pregnancy did not happen.

## **6. STATISTICAL ANALYSES**

Note that standard data derivation rule and stat methods are described in annex 1 (Section 11).

### **6.1. Demography**

#### **6.1.1. Analysis of demographics/baseline characteristics planned in the protocol**

Demographic and baseline characteristics such as age at enrolment, sex, race, ethnicity and smoking status will be summarised by study group using descriptive statistics, for the Exposed Set:

- Frequency tables will be generated for categorical variable such as sex, race, ethnicity, age category, smoking status;
- Mean, median, standard deviation, minimum and maximum will be provided for continuous data such as age and pack-years of smoking.

The following variables will be included in demography summary and listings:

- Age in year
- Age category: 40-59 y, 60-80y
- Gender: Male, Female
- Race: (all reported in e-CRF)
- Ethnicity: Hispanic or Latino, Not Hispanic nor Latino
- Pack-years of smoking
- Smoking status

While, additionally, the following vital signs will be tabulated as baseline characteristics:

- Height (cm)
- Weight (kg)
- Body temperature
- Heart rate
- Respiratory rate
- Systolic Blood Pressure
- Diastolic Blood Pressure,

**CONFIDENTIAL**207759 (NTHI MCAT-008)  
Statistical Analysis Plan Amendment 1 Final

Demographic table will be also presented for All enrolled set, if differs from ES.

The distribution of subjects enrolled among the study sites will be tabulated as a whole and per study group.

Withdrawal status will be summarised by group using descriptive statistics:

- The numbers of withdrawn subjects will be tabulated according to the reason for withdrawal;
- The number of subjects enrolled into the study as well as the number of subjects excluded from the different analysis sets will be tabulated.

No inferential analyses of demographic data are planned.

**6.1.2. Additional considerations****6.1.2.1. Vaccination and Medical History**

The frequencies and percentages of subjects with medical history and by MedDRA body system and preferred term will be presented overall and by vaccine group.

**6.2. Exposure****6.2.1. Analysis of exposure planned in the protocol**

The number of vaccinations the subjects will receive will be tabulated for each study group.

**6.3. Efficacy/Effectiveness****6.3.1. Analysis of efficacy planned in the protocol**

Not Applicable.

**6.3.2. Additional considerations**

Not Applicable.

**6.4. Immunogenicity****6.4.1. Analysis of immunogenicity planned in the protocol**

The analysis will be performed on the PPS at first line. If the percentage of vaccinated subjects with serological results excluded from the PPS is more than 10%, a second line analysis will be performed on the FAS.

The CMI analysis will be performed on the FAS – CMI Subset.

**CONFIDENTIAL**207759 (NTHI MCAT-008)  
Statistical Analysis Plan Amendment 1 Final**6.4.1.1. Humoral Immunogenicity****6.4.1.1.1. Within groups assessment****ELISA**

For each group, eight timepoints (Day 1, Day 91, Day 181, Day 211, Day 361, Day 391, Day 541 and Day 721, when blood samples are collected) are considered for humoral immune response against the four antigens PD, PE, PilA and UspA2, for which the following will be computed:

- Seropositivity rate and associated 95% CI at each time point (See Additional considerations for seroresponse definition and assay cut-off values).
- GMCs at each time point and their 95% CIs.

With respect to antibody levels at Day 1 (before 1st dose):

- GMRs at each time point and their 95% CIs.
- Percentage of subjects with 2-fold, 4-fold and 8-fold increase at each time point and associated 95% CI.

With respect to antibody levels at Day 181 (before 3rd dose):

- GMRs at Day 211, Day 361, Day 391, Day 541 and Day 721 and their 95% CIs.
- Percentage of subjects with 2-fold, 4-fold and 8-fold increase at Day 211, Day 361, Day 391, Day 541 and Day 721 and associated 95% CI.

With respect to antibody levels at Day 361 (before 4th dose):

- GMRs at Day 391, Day 541 and Day 721 and their 95% CIs.
- Percentage of subjects with 2-fold, 4-fold and 8-fold increase at Day 391, Day 541 and Day 721 and associated 95% CI.

The distribution of antibody concentrations will be displayed using Reverse Cumulative Curves.

**6.4.1.1.2. Between groups assessment**

Comparative analyses will be exploratory with the aim to characterise the difference between groups in humoral immune response.

At each visit, the group difference in terms of GMCs and GMRs (except at Day 361) will be evaluated, by computing GMC and GMR ratio, between the two groups, and their associated two-sided 95% CIs.

Differences in percentages of subjects with ELISA concentration > 'Assay cut-off' between the groups will be also calculated with the associated two-sided 95% CIs.

**CONFIDENTIAL**207759 (NTHI MCAT-008)  
Statistical Analysis Plan Amendment 1 Final**6.4.1.2. Cell-mediated immune response**

CMI induced by the NTHi-Mcat candidate vaccine will be evaluated presenting the frequencies (including mean, medium, minimum and maximum) of antigen-specific CD4+ /CD8+ T cells per 10^6 cells. The specific CD4+ / CD8+ T cells being identified as the CD4+ / CD8+ T cells expressing at least 2 different cytokines/activation markers among CD40 Ligand (CD40L), IL-2, TNF- $\alpha$ , IFN- $\gamma$ , IL-13 and IL-17 upon *in vitro* stimulation will also be evaluated. Descriptive statistics (Min, Q1, Median, Q3 & Max) will be reported for each group at Day 1, Day 91, Day 181, Day 211, Day 361 and Day 391.

**6.4.1.3. T helper profile**

T helper profile of the specific CD4+ and CD8+ T cells response will be evaluated with the frequencies of antigen (stimulation) specific CD4+ / CD8+ T-cells expressing T helper 1, T helper 2 and T helper 17 specific markers (IFN- $\gamma$ , IL-13 and IL-17 respectively) and will be summarised by means of descriptive statistics (mean, SD, minimum, Q1, median, Q3, and maximum) for each group and at Day 1, Day 91, Day 181, Day 211, Day 361 and Day 391.

**6.4.2. Additional considerations****6.4.2.1. Humoral Immunogenicity**

- Calculation of the GMCs will be performed by taking the anti-logarithm in base 10 (anti-log10) of the mean of the log10 ELISA concentration.
- Antibody concentrations below the assay cut-off will be given an arbitrary value of half the assay cut-off for the purpose of geometric mean concentration (GMC) calculation.
- A seronegative subject is defined as a subject whose antibody concentration is below the assay cut-off value (i.e. the ELISA lower limit of quantification). Specifically, the assay cut-off values are defined as follows:

*Anti-PD antibodies: 153 EU/mL*

*Anti-PE antibodies: 16 EU/mL*

*Anti-PilA antibodies: 8 EU/mL*

*Anti-UspA2 antibodies: 28 EU/mL*

Assay cut-off and unit might be subject to change during the study (e.g. in case of assay re-optimization, qualification, (re)validation or standardization). In this case, this will be documented in the clinical study report.

- A seropositive subject is defined as a subject whose antibody concentration is greater than or equal to the assay cut-off value (i.e. the ELISA lower limit of quantification).
- For a given subject and analysis of a given immunogenicity measurement, missing or unevaluable measurements will not be replaced.

**CONFIDENTIAL**207759 (NTHI MCAT-008)  
Statistical Analysis Plan Amendment 1 Final

- The percentage of seropositive subjects and associated two-sided 95% Clopper-Pearson [1] confidence intervals (CIs) will be computed by vaccine group at each visit.
- The 95% CIs for the difference between the percentages of seropositive subjects will be computed using Miettinen and Nurminen method [2] which has superior performance characteristics when rates are close to 0 or close to 1 and when compared to those formed from the Wald statistic.
- GMCs for each group and their ratios at each post-exposure timepoint will be calculated by fitting an ANCOVA model including the country, age category (40 - 59 years or 60 - 80 years) and smoking status (current or former smokers) as factors and pre-Dose 1 concentration (as covariate).

The SAS statements that will be used to calculate the adjusted GMC will be similar to:

```
PROC glm;
  BY timepoint antibody;
  CLASS country age smoking_status group;
  MODEL logtiter= log_baseline country age smoking_status group;
  LSMEANS group / tdiff stderr cl pdiff;
RUN;
```

In addition, the GMRs for each group and their ratios between study visit (timepoints) and the baseline measure will be calculated by fitting an ANOVA model on the log10 of the titer ratio between a generic visit x and the baseline visit. This model will include the country, age category (40 - 59 years or 60 - 80 years) and smoking status (current or former smokers) as factors.

The SAS statements that will be used to calculate GMRs between timepoints will be similar to:

```
PROC glm;
  BY timepoint antibody;
  CLASS country age smoking_status group;
  MODEL log(titer_visitx/baseline)= country age
  smoking_statusgroup;
  LSMEANS group / tdiff stderr cl pdiff;
RUN;
```

The same approach will be used to compute GMRs with respect to the humoral immune response at Day 181 and at day 361: in these cases, baseline refers to, respectively, Day 181 and Day 361 concentration.

GMCs and GMRs will be obtained by exponentiating the estimate of the log-ratio for each group.

**CONFIDENTIAL**207759 (NTHI MCAT-008)  
Statistical Analysis Plan Amendment 1 Final**6.4.2.2. Cell Mediated Immunity**

- The frequency of **antigen-specific** CD4+ or CD8+ T-cells for each individual subject is calculated as the difference between the frequency of CD4+ or CD8+ T-cells producing at least 2 cytokines among IFN- $\gamma$ , IL-2, IL-13, IL-17, TNF- $\alpha$  and/or CD40L, upon *in vitro* stimulation with the antigen (induction condition) minus the frequency of CD4+ or CD8+ T-cells producing at least 2 cytokines upon *in vitro* stimulation in medium only (background condition). For descriptive statistics purposes, differences less or equal to zero (0) are imputed to 1.

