**5.2.2.2.1. Study group allocation**

The target will be to enrol approximately 200 eligible subjects who will be randomly assigned to two study groups in a (1:1) ratio (approximately 100 subjects in each group).

Allocation of the subject to a study group at the investigator site will be performed using a randomisation system on internet (SBIR).

After obtaining the signed and dated ICF from the subject and having checked the eligibility of the subject, the site staff in charge of the vaccine administration will access SBIR. Upon providing the subject identification number, the randomisation system will determine the study group and will provide the treatment number to be used for the first dose.

The number of each administered treatment must be recorded in the eCRF on the Vaccine Administration screen.

When SBIR is not available, please refer to the SBIR user guide or the Study Procedures Manual (SPM) for specific instructions.

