**Secondary objectives:****Humoral immunogenicity after third dose**

The intent of this secondary objective is to evaluate the improvement of the persistence of antibody response at one month after a third injection. An increase in the antibody titres compared to the second dose is expected.

Approximately a 10% drop out is expected for the third dose evaluation (given at 6 months for one arm and at 12 months for the other arm) and thus 90 evaluable subjects are expected to be analysed for the humoral immunogenicity evaluation.

A sample size of 90 evaluable subjects achieves 90% power to detect a difference of 0.256 between the null hypothesis mean of 0.0 and the alternative hypothesis mean with a known standard deviation of 0.83 and with a significance level (alpha) of 0.05 using a one-sided one-sample t-test.

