## 2. STUDY DESIGN

**Figure 1 Study design overview**

**Experimental design:** Phase II, observer-blind, randomised, multi-centric study with two parallel groups.

**Duration of the study:** for each subject enrolled, the study will last approximately 2 years from Visit 1 (enrolment visit):

- Epoch 001 : Primary (Vaccination phase) starting at Visit 1 (Day 1) and ending at Visit 9 (Day 541).
- Epoch 002 : Long-term follow-up starting after Visit 9 (Day 541) and ending at Visit 10 (Day 721).

Primary Completion Date (PCD): Visit 9 (Day 541).

Refer to the Glossary of terms of the protocol for the definition of PCD.

**End of Study (EoS):** Last testing results released of samples collected at Visit 10 (Day 721).

Refer to the Glossary of terms of the protocol for the definition of EoS.

**CONFIDENTIAL**207759 (NTHI-MCAT-008)  
Statistical Analysis Plan Amendment 1 Final

Study groups:

- **Schedule 1** : Approximately 100 subjects receiving three doses of the AS01E-adjuvanted GSK Biologicals' NTHi-Mcat investigational vaccine containing 10 µg of PD, 10 µg of PE-PilA, and 3.3 µg of UspA2 at Visit 1 (Day 1), Visit 3 (Day 61) and Visit 5 (Day 181) and one dose of placebo at Visit 7 (Day 361).
- **Schedule 2** : Approximately 100 subjects receiving three doses of the AS01E-adjuvanted GSK Biologicals' NTHi-Mcat investigational vaccine containing 10 µg of PD, 10 µg of PE-PilA, and 3.3 µg of UspA2 at Visit 1 (Day 1), Visit 3 (Day 61) and Visit 7 (Day 361) and one dose of placebo at Visit 5 (Day 181).

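### Within-schedule GMR intervals for the third-dose contrasts use one variance pooled over a just-vaccinated arm and a placebo arm, and lose 95% coverage if the two SDs differ

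*SAP*

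**What the plan says.** SAP Section 6.4.1.1.1 asks, within each group, for geometric mean ratios (GMRs) against three reference days. Against Day 181 it lists "GMRs at Day 211, Day 361, Day 391, Day 541 and Day 721 and their 95% CIs", and against Day 361 it lists Day 391, Day 541 and Day 721. SAP Annex 1 (11.2.4) makes every CI two-sided 95%.

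The only method given for these ratios is in SAP Section 6.4.2.1: "the GMRs for each group and their ratios between study visit (timepoints) and the baseline measure will be calculated by fitting an ANOVA model". The model code there is PROC GLM, run by timepoint and antibody. Group is a CLASS factor beside country, age category and smoking status, and the per-group intervals come from LSMEANS with the `cl` option. The section extends the same approach to the Day 181 and Day 361 references. It names no group-specific variance, robust standard error or check for unequal spread.

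The schedules differ exactly at those references. Under SAP Section 2, Schedule 2 receives "one dose of placebo at Visit 5 (Day 181" when Schedule 1 receives vaccine; at Day 361 the products are reversed.

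**The concern.** PROC GLM has one residual mean square per fit. With both schedules in the fit, each schedule's own interval is built from the average of the two arms' variances. That is harmless when the arms vary alike, and the one-month third-dose contrasts are where this is least assured. In the placebo arm the log ratio over those 30 days reflects waning and assay noise. In the vaccinated arm it also carries subject-to-subject differences in the boost. The rule that sets values below the cut-off to half the cut-off (SAP 6.4.2.1) works the same way: a subject below the cut-off at both visits contributes a log ratio of exactly zero, which is more likely without a booster.

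At stake is the calibration of the within-schedule interval around the rise after the third dose. SAP Section 7 says the analyses are meant to estimate the response after the third injection, and SAP 6.4.1.1.2 makes the between-group work exploratory. The pooled model thus serves the exploratory contrast well and may misstate the uncertainty of the within-schedule estimate.

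**Working it through.** **The plan's own figure.** Protocol Section 10.4 gives: "A sample size of 90 evaluable subjects achieves 90% power to detect a difference of 0.256", "with a known standard deviation of 0.83 and with a significance level (alpha) of 0.05 using a one-sided one-sample t-test". The 90 comes from 100 per schedule, since "Approximately a 10% drop out is expected for the third dose evaluation". Power = Φ(0.256 × √90 / 0.83 − 1.645) = Φ(2.926 − 1.645) = 0.900; the noncentral t gives 0.896. The figure reproduces. The calculation is within one arm.

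**Inputs for the check.**
- n = 90 per arm (Protocol 10.4). Allocation is equal: subjects are "randomly assigned to two study groups in a (1:1) ratio" (Protocol 5.2.2.2.1).
- Vaccinated-arm SD s₁ = 0.83. This is the only SD in the documents. Using it for this log ratio is an assumption, and it affects only the absolute half-widths.
- Placebo-arm SD s₂ = r × s₁. The documents give no value for r, so a range is shown.

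**Formulas, leaving out the covariates.**
- Own-arm half-width: t(0.975, 89) × s₁ / √90 = 0.174.
- Pooled half-width: t(0.975, 178) × √((s₁² + s₂²)/2) / √90.
- Their ratio is close to √((1 + r²)/2), so the relative error depends on r and not on 0.83 or the base of the logarithm.
- Vaccinated-arm coverage: 2Φ(pooled half-width × √90 / s₁) − 1.

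Example, r = 0.5: s₂ = 0.415 and √((0.6889 + 0.1722)/2) = 0.656, so the pooled half-width is 0.136 and the ratio to 0.174 is 0.785.

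| r | Pooled half-width | Pooled / own, vaccinated arm | Coverage, vaccinated arm | Pooled / own, placebo arm |
|---|---|---|---|---|
| 1.25 | 0.195 | 1.12 | 97.4% | 0.90 |
| 1.0 | 0.173 | 0.99 | 95.2% | 0.99 |
| 0.8 | 0.156 | 0.90 | 92.6% | 1.12 |
| 0.7 | 0.149 | 0.86 | 91.1% | 1.22 |
| 0.5 | 0.136 | 0.785 | 88.1% | 1.57 |
| 0.3 | 0.127 | 0.73 | 85.5% | 2.44 |

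With equal arms the narrowing cannot exceed about 30% (1/√2 = 0.707), so coverage stays at or above about 83-84%.

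**With the SAP's factors in the model.** LS-mean intervals were simulated with country, age and smoking terms, 3,000 runs per setting. The country mixes are assumptions.

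| r | Vaccinated-arm coverage, two balanced countries | Vaccinated-arm coverage, four unequal countries |
|---|---|---|
| 1.0 | 95.1% | 94.3% |
| 0.7 | 91.1% | 91.8% |
| 0.5 | 87.8% | 89.7% |
| 0.3 | 85.7% | 87.5% |

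**Between-schedule ratio.** With equal arms the pooled variance of the difference is 2/n × (s₁² + s₂²)/2 = (s₁² + s₂²)/n, which is the correct value whatever r is. Simulated coverage was 94.6% to 95.1%.

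**The case against.** The strongest reply is that the narrowing is conditional. The documents give no arm-specific SD for any log ratio. With equal SDs nothing is wrong, and if the placebo arm varied more, the vaccinated arm's CI would be too wide. This stands. A reader might infer from the code alone that the interval is too narrow; the code shows only that the variance is pooled, and the direction is an expectation about the data.

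A reader might also infer that the humoral sample size was argued on this contrast and that the protocol planned to report a one-sample t interval. Protocol 10.4 does not support that. It never names the contrast behind 0.256 and 0.83, and its reference to a rise over the second dose could mean Day 91 and not Day 181. The one-sample test is a planning device.

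Nor do the documents make this GMR the leading humoral result. The endpoints are antibody concentrations and seropositivity. Seropositivity rates have their own Clopper-Pearson intervals, and the fold-increase percentages and reverse cumulative curves do not use the pooled variance. No decision rule depends on the GMR interval, and the code is offered only as similar to what will be run.

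The calculations concern log ratios relative to Day 181 and Day 361, so they say nothing firm about GMCs. For GMRs relative to Day 1, both arms carry the response to two earlier doses and the SDs may be closer.

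What remains is that the plan gives one method for these intervals, that method assumes equal variances, and the assumption is weakest where the arms have just received different products.

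**Conclusion.** The point holds in conditional form. The Day 211/Day 181 and Day 391/Day 361 within-schedule CIs use a variance pooled over a vaccinated and a placebo arm. If the vaccinated arm's log ratio has the larger SD, its CI is too narrow and the placebo arm's too wide. For 90 per arm and an assumed r of 0.8, 0.5 and 0.3, the vaccinated arm's CI is about 10%, 22% and 27% too narrow, with coverage of about 93%, 88-90% and 86-87%. At r = 1 there is no error; above 1 the sign reverses. The between-schedule ratio is sound at 1:1 allocation. The consequence is modest, since the analysis is secondary and descriptive, but the intervals are promised as 95% and the repair is cheap.

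**What to change.** In SAP Section 6.4.2.1, for the GMRs relative to Day 181 and Day 361, keep the joint model with country, age category, smoking status and group, but let the residual variance differ by group. PROC MIXED with `REPEATED / GROUP=group` and Satterthwaite degrees of freedom does this. Report the within-schedule GMR CIs from that fit.

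This is preferable to the two obvious alternatives. A one-sample t interval per arm would drop the SAP's covariate adjustment and so estimate something different. Separate adjusted models per arm cost precision: in the four-country simulation at r = 1 the pooled interval was 0.90 times the separate-model one, so separate fitting widens it by about 10%.

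The cost is one SAP sentence and a small code change, with no new data. The vaccinated arm's CI becomes somewhat wider if its SD is the larger. If the variances prove equal, the result will be nearly the same as under the current plan.
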